	8.5 Written Informed Consent	
	8.6 Process of Consent	37
	8.7 Certificate of Confidentiality	38
Q	References	35

1. Protocol Synopsis

Interventional Synopsis

Protocol Title: Pilot Clinical Drug Trial of Sirolimus for Cognitive Impairments in Sturge-Weber syndrome Study Chair: [name] Statistician: [name] Consortium: The Brain Vascular Malformations Clinical Research Network: Predictors of Clinical Course Participating Sites: Kennedy Krieger Institute, Johns Hopkins School of Medicine, Cincinnati Children's Hospital Medical Center Activation Date: June 22, 2016 Current Status: Active Sample Size: 10 (not including subjects screened or early withdrawals within first 2 months on study drug) Recruitment goal of five subjects from the Kennedy Krieger Institute and five subjects from Cincinnati Children's Hospital Medical Center. If Cincinnati Children's Medical Center (CCHMC) is unable to meet their recruitment goal,
syndrome Study Chair: [name] Statistician: [name] Consortium: The Brain Vascular Malformations Clinical Research Network: Predictors of Clinical Course Participating Sites: Kennedy Krieger Institute, Johns Hopkins School of Medicine, Cincinnati Children's Hospital Medical Center Activation Date: June 22, 2016 Current Status: Active Sample Size: 10 (not including subjects screened or early withdrawals within first 2 months on study drug) Recruitment goal of five subjects from the Kennedy Krieger Institute and five subjects from Cincinnati Children's Hospital Medical Center. If Cincinnati
Study Chair: [name] Statistician: [name] Consortium: The Brain Vascular Malformations Clinical Research Network: Predictors of Clinical Course Participating Sites: Kennedy Krieger Institute, Johns Hopkins School of Medicine, Cincinnati Children's Hospital Medical Center Activation Date: June 22, 2016 Current Status: Active Sample Size: 10 (not including subjects screened or early withdrawals within first 2 months on study drug) Recruitment goal of five subjects from the Kennedy Krieger Institute and five subjects from Cincinnati Children's Hospital Medical Center. If Cincinnati
Statistician: [name] Consortium: The Brain Vascular Malformations Clinical Research Network: Predictors of Clinical Course Participating Sites: Kennedy Krieger Institute, Johns Hopkins School of Medicine, Cincinnati Children's Hospital Medical Center Activation Date: June 22, 2016 Current Status: Active Sample Size: 10 (not including subjects screened or early withdrawals within first 2 months on study drug) Recruitment goal of five subjects from the Kennedy Krieger Institute and five subjects from Cincinnati Children's Hospital Medical Center. If Cincinnati
Consortium: The Brain Vascular Malformations Clinical Research Network: Predictors of Clinical Course Participating Sites: Kennedy Krieger Institute, Johns Hopkins School of Medicine, Cincinnati Children's Hospital Medical Center Activation Date: June 22, 2016 Current Status: Active Sample Size: 10 (not including subjects screened or early withdrawals within first 2 months on study drug) Recruitment goal of five subjects from the Kennedy Krieger Institute and five subjects from Cincinnati Children's Hospital Medical Center. If Cincinnati
Clinical Course Rennedy Krieger Institute, Johns Hopkins School of Medicine, Cincinnati Children's Hospital Medical Center Activation Date: June 22, 2016 Current Status: Active Sample Size: 10 (not including subjects screened or early withdrawals within first 2 months on study drug) Recruitment goal of five subjects from the Kennedy Krieger Institute and five subjects from Cincinnati Children's Hospital Medical Center. If Cincinnati
Children's Hospital Medical Center Activation Date: June 22, 2016 Current Status: Active Sample Size: 10 (not including subjects screened or early withdrawals within first 2 months on study drug) Recruitment goal of five subjects from the Kennedy Krieger Institute and five subjects from Cincinnati Children's Hospital Medical Center. If Cincinnati
Activation Date: June 22, 2016 Current Status: Active Sample Size: 10 (not including subjects screened or early withdrawals within first 2 months on study drug) Recruitment goal of five subjects from the Kennedy Krieger Institute and five subjects from Cincinnati Children's Hospital Medical Center. If Cincinnati
Current Status: Active Sample Size: 10 (not including subjects screened or early withdrawals within first 2 months on study drug) Recruitment goal of five subjects from the Kennedy Krieger Institute and five subjects from Cincinnati Children's Hospital Medical Center. If Cincinnati
Sample Size: 10 (not including subjects screened or early withdrawals within first 2 months on study drug) Recruitment goal of five subjects from the Kennedy Krieger Institute and five subjects from Cincinnati Children's Hospital Medical Center. If Cincinnati
study drug) Recruitment goal of five subjects from the Kennedy Krieger Institute and five subjects from Cincinnati Children's Hospital Medical Center. If Cincinnati
Recruitment goal of five subjects from the Kennedy Krieger Institute and five subjects from Cincinnati Children's Hospital Medical Center. If Cincinnati
subjects from Cincinnati Children's Hospital Medical Center. If Cincinnati
I ('mildren's Riedical i enter (L') 'HRR(') is unable to meet their recruitment doal
then Kennedy Krieger Institute (KKI) may enroll additional participants to meet
the overall sample size of 10.
Target Enrollment October 1, 2016 – December 1, 2018 Period:
Primary Study 1) To gain a preliminary understanding of the safety and 2) determine best
Objective: outcomes to be used to assess the utility of sirolimus for the treatment of
cognitive impairments in Sturge-Weber syndrome (feasibility of full-scale
research design)
Study Population Patients with Sturge-Weber syndrome brain involvement as defined on
and Main Eligibility/ neuroimaging (n=10 subjects, male and female, ages 3 to 31 years) and the
Exclusion Criteria: following:
A A
1. Male or female patients ages 3 to 31 years of age.
Cognitive impairment as defined by the following:
 SWS cognitive neuroscore of ≥ 1
Ability to participate in direct neuropsychological and developmental
testing.
4. English as primary language.
5. Stable anti-epileptic drugs (no changes in medications except dose for
>3 months).
6. Adequate renal function. GFR must be greater than 50 ml/min/m2 as
determined by the Schwartz Formula for children and MDRD for adults:
 http://www.nkdep.nih.gov/professionals/gfr_calculators/i
ndex.htm
7. If female and of child bearing potential, documentation of a negative
pregnancy test prior to enrollment determined by a urine test is required.
Sexually active pre-menopausal female patients (and female partners of
male patients) must use adequate contraceptive measures, excluding
estrogen containing contraceptives, while on the study drug. Abstinence
will be considered an adequate contraceptive measure.
Q IND <1 ⊑ / Anticonggulation in allowed it towns thiD < 1 ⊑ an a stable data
8. INR ≤1.5 (Anticoagulation is allowed if target INR ≤ 1.5 on a stable dose
of warfarin or on a stable dose of LMW heparin for >2 weeks.)
of warfarin or on a stable dose of LMW heparin for >2 weeks.) 9. Adequate liver function as shown by:
of warfarin or on a stable dose of LMW heparin for >2 weeks.)

- 10. Written informed consent according to local guidelines. Local guidelines for subject assent will also be followed.
 11. Stable dose of medications affecting the cytochrome P 450 3A4 (CYP3A4) and p glycoprotein (P gp) systems for at least 3 months prior to consent.

Treatment				
Agent-	Rapamune® / Rapamycin® (sirolimus)			
Dosage,	Oral dose targeting a serum level dose range of 4-6 ng/mL given for a minimum of			
schedule, route of	six months. Dose based on surface age, surface area, and mini-PK as outlined in			
administration-	the protocol.			
	Subjects will receive no more than 2 mg/day given in two divided doses for a			
1	minimum of six months with the option to enter into the Extension Phase up to an			
	additional year and a half.			
Primary	Safety and Tolerability of sirolimus in patients with Sturge-Weber syndrome.			
Outcome	Adverse Events will be determined at every visit and on every phone call			
Measures:	using a case report with a list of side effects which can be seen with higher			
	doses and serum levels than are expected with this study. Impact of the			
	study drug upon seizure frequency, type, and duration will be assessed by			
	patient/parent report using a seizure report form we have used in a prior study. Impact of study drug upon neurologic, ophthalmologic, endocrine,			
	medical rehab, and dermatologic status will be assessed with case report			
	forms, the physical exam, the Sturge-Weber syndrome neuroscore, the port-			
	wine birthmark score, and other outcome measures described in the			
	protocol.			
	Change over six months in cognitive functioning in Sturge-Weber syndrome			
	is the primary outcome measure. This outcome will be assessed using a			
	panel of testing selected based upon extensive experience in testing			
	cognitive function in adults and children with SWS at the Kennedy Krieger			
	Sturge-Weber Center. These will include the following measures from the			
	National Institute of Health Toolbox (Gershon et al., 2010):			
	Attention/Executive Function – Flanker Inhibitory Control and Attention Test (Eriksen & Eriksen, 1974)			
	Executive Functioning – Dimensional Change Card Sort Test (Zelazo, Frye, & Rapus,1996)			
	Episodic Memory – Picture Sequence Memory Test (Bauer et al., 2013; Dikmen et al., 2014)			
	GL al., 2014)			
	Language – Oral Reading Recognition Test			
	Language – Picture Vocabulary Test (Dunn & Dunn, 1981)			
	Processing Speed – Pattern Comparison Processing Speed Test (Carlozzi et al., 2014)			
	Working Memory – List Sorting Working Memory Test (Weintraub et al., 2013)			
	Dexterity – 9-hole Pegboard Dexterity Test (Wang, Bohannon, Kapellusch, Garg, & Gershon, 2015)			
	 Strength – Grip Strength Test (Hamilton, Balnave, & Adams, 1994)			
	odoligin - Olip odoligin rest (riaminton, Dalliave, & Adams, 1994)			

PROMIS measures self-report of emotional functioning (Cella et al., 2007)

Each test in this panel is age normed. Therefore even though subjects will be of different ages, the change in their performance as a percentage of the normed values will be relevant and comparable from subject-to-subject. There are also published test-retest standard deviations from which to ascertain how much of a change in score is needed for a change to be regarded as significant.

Secondary Outcome Measures:

Secondary outcome measures include: change in quantitative EEG (power asymmetry), SWS clinical neuroscore, and birthmark score.

Another secondary outcome measure will be an assessment of impact upon seizures. Parents/caregivers will report the following before starting study drug and at each visit:

- Number of seizures (specifically motor seizures) This is the most reliable and important seizure outcome.
- Seizure duration
- Seizure Type
- Number of episodes of status epilepticus, defined as generalized convulsive seizure lasting longer than 10 minutes
- Number of uses of rescue medication.
- Number of ER visits/ hospitalizations for seizures

Statistical Considerations (sample size and analysis plan):

Results of the above tests will be compared to age normed values. In addition, the difference in results between final test results and initial test results will be obtained for the cognitive functioning score of each subject. Mean and standard deviation of this difference for all 10 subjects will be calculated. These results will be used to determine whether individuals and the group as a whole demonstrated age normed changes in their cognitive functioning over the course of the six month trial. Neuropsychological testing will occur at both sites, KKI and CCHMC, and the deidentified results will be sent to KKI for analysis. There is no control group in this study of subjects who are not receiving study drug. The published test-retest standard deviations will be used to determine whether changes in testing results exceed expected test-retest changes in results.

Expected seizure rate can vary greatly both between subjects and for an individual. Subjects must be on the same AEDs for the past three months to join the study. Subjects whose seizures increase to the point where it is necessary to add another seizure medication, start the ketogenic or Atkins diet, or go for surgery to control their seizures will be removed from the study.

Quantitative EEG: An EEG will be done prior to starting study drug and at the end of the study while still on study drug. An asymmetry in power (roughly an integration of amplitude and frequency) in the affected side of the brain compared to the unaffected (or less affected) side of the brain, will be quantified as previously described (Hatfield et al., 2007; Ewen et al., 2009) for the quantitative EEG analysis. EEGs will occur at both sites, KKI and CCHMC, and the de-identified EEGs will be sent to KKI for analysis. The reason for this analysis is as a non-invasive biomarker of brain function which could be useful to develop as a marker of drug response. Quantitative EEG power analysis reflects an integration of the EEG activity amplitude and frequency. Therefore asymmetry of power on qEEG for these subjects reflects the increased slowing and decreased amplitude frequently seen in these patients interictally as their neurologic involvement progresses. Even patients with bilateral brain involvement have more involvement on one side than on the other side. Power asymmetry on qEEG has been shown to correlate with brain perfusion, brain atrophy, and SWS neuroscore, therefore, it has the potential as a biomarker responsive to

monitor sirolimus treatment, both from the standpoint of safety and efficacy in a future larger clinical trial.

Seizure (motor seizures) number will be collected at each study visit and compared across visits. Seizure number will be recorded from the two months prior to joining the study at baseline (by history) and "since last visit" for all study visits. Seizure length and type, need for rescue medication, ER visit or hospitalization will also be recorded and compared across visits and at the end of the study (on drug) compared to the beginning of the study (prior to starting drug). There will be stopping rules for safety.

Clinical neurologic severity scores (neuroscores) will be collected at each study visit, using a scale developed and validated by KKI. The neuroscore is comprised the frequency of seizures, extent of hemiparesis, assessment of visual field cut, and degree of cognitive functioning with a total score of 15 possible (Kelly, Hatfield, Lin, & [name], 2005). Descriptive statistics for this measure will be reported in the form of median and range. Mann Whitney U Test will be used to assess whether a significant change in neuroscores has occurred after treatment compared to prior to treatment. Neuroscores will be collected at both sites, KKI and CCHMC, and the de-identified results will be sent to KKI for analysis.

The Neurologic Quality of Life (Neuro QoL) will be collected prior to starting study drug and at each study visit. Descriptive statistics for this measure will be reported in the form of median and range. Mann Whitney U Test will be used to assess whether a significant change in quality of life has occurred after treatment compared to prior to treatment. NeuroQoL will be collected at both sites, KKI and CCHMC, and the deidentified results will be sent to KKI for analysis.

The quantification of the facial birthmark score developed and validated at the KKI will occur at the beginning of the study, prior to starting study drug, and when the subjects reach the endpoint of the study at six months' time while still on study drug (Waelchli et al., 2014). If the subject elects to enter the Extension Phase, the facial birthmark will be rated at each Extension Phase visit. Descriptive statistics for this measure will be reported in the form of median and range. Mann Whitney U Test will be used to assess whether a significant change in the facial birthmark has occurred after treatment compared to prior to treatment. Facial birthmark scoring will occur at both sites, KKI and CCHMC, and the de-identified results will be sent to KKI for analysis.

Biomarker Development: Spearman's rho will be used to assess for the strength, direction and significance of correlations between qEEG results and neuropsychological outcomes, NeuroQoL and the SWS Neuroscore. Significance will be taken at p<0.05.

All of these outcomes will be used to determine whether sirolimus is 1) sufficiently well tolerated in this small group of subject and 2) what outcome measures and biomarkers demonstrate preliminary evidence of being responsive to sirolimus. This information will be used to determine the advisability of proceeding with a larger multicentered study and aid in the selection of outcome measures and biomarkers to be part of that follow-up randomized placebo-controlled trial.

Sponsors (federal, state, foundation and industry support): National Institute of Health (NIH) Faneca 66 Foundation

Pfizer (study drug only)

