4.3 Recruitment of Participants

Recruitment for the initial pilot will be from the Hunter Nelson Sturge-Weber Center database at the Kennedy Krieger Institute and from the Vascular Anomalies clinic at Cincinnati Children's Sturge-Weber syndrome database. Patients who are in research databases and have given the study team at the Kennedy Krieger Institute permission to contact them regarding research will be sent information regarding the trial and invited to contact the study team for more information if interested. Patients coming for clinical visits to either [name] or [name] clinics will be pre-screened for meeting inclusion criteria. A log will be kept of patients pre-screened for this trial and results of the pre-screening process.

Information about the pilot study will also be posted on the center websites, clinicaltrials.gov, the NIH Brain Vascular Malformation website, and offered for posting on the websites of relevant advocacy foundations. Participants will be either [name] or [name] patients. If interested, individuals will contact [name] or [name] from the website postings and will be seen first for a clinical visit. The investigational nature and objectives of this trial, the procedures, the treatments involved, the attendant risks, and discomforts, as well as potential alternative therapies, will be carefully explained to the patient or their parents or guardian if he/she is a child. A signed informed consent document will be obtained after the entirety of the pilot study is explained. Consent will be obtained by the site PI or an associate investigator on the trial. Where deemed appropriate by the clinician and the child's parents or guardian, the child will also be included in all discussions about the trial. Assent will be obtained from all children able to provide assent according to our local IRB guidelines. Our consent contains an assent statement on the second-to-last page. The goal is to recruit up to ten participants total in this pilot study, with a recruitment goal of five subjects from the Kennedy Krieger Institute and five subjects from Cincinnati Children's Hospital Medical Center. If CCHMC is unable to meet their recruitment goal, then KKI may enroll additional participants to meet the overall sample size of 10.

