5.7 Subject Discontinuation

All data acquired prior to termination for the reasons outlined below will be included in the primary analysis unless patient withdraws consent. Every effort will be made to conduct a final study visit with the participant and participants will be followed clinically until, if applicable, all adverse events resolve.

- Withdrawal of consent
- Withdrawal by the participant
- Withdrawal by the investigator
- Intercurrent illness or event that precludes further visits to the study site or ability to evaluate disease (for example, mental status change, large pleural effusion, large stroke).

Early Stopping Rules: If a participant experiences a significant decline in his or her health or wellbeing, the PIs may remove the participant from the pilot study. This decision will be promptly made on a case-by-case basis with careful discussion between the PIs, the parents and/or patient, and in consultation with the IRB. In some cases, it can be more medically destabilizing to remove the subject from the study drug. However, in any case where a significant decline in health may be attributable to the study drug, or in any case where it is determined that it may not be in the subject's best interest to remain on the study drug, then they will be removed from the study. A significant decline in health or wellbeing could include a loss of seizure control and/or the occurrence of intolerable side effects. Loss of seizure control is defined as an increase in seizure frequency and/or severity or use of emergency medications that warrant the initiation of a new seizure medication or treatment such as, Ketogenic/Atkins diet, surgery, or VNS. If there has been a loss of seizure control, then the subject will be removed from the study drug at that time, he or she will complete the ending assessments, and then the subject will be removed from the trial. Other stopping criteria are listed in Tables 1 and 2 above. Other removal criteria include: death, lost to follow-up, withdrawal of consent for any further data submission, or inability to complete follow up two years from the protocol completion. Early withdrawals within the first two months on the study drug will be replaced with a new study subject.

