5.9 Quality Control: Study Related Procedures

- 1. Clinical coordinators at both sites will review the case report forms after completion by [name] or [name] to resolve any issues.
- 2. [name] and [name] will review the study progress regularly with monthly phone conferences. The two sites will have internal reviews performed regularly to ensure high quality of the study procedures and subsequent data.
- 3. The DMCC will perform an audit of the overall protocol including this pilot project.

6. Statistical Considerations

The proposed trial is a pilot drug trial. Based on the results, a sample size calculation will be done, using the cognitive outcome with the greatest response to the study drug, to plan a follow up randomized, placebo-controlled trial, should one be warranted. If no serious adverse events which are thought to probably or possibly be due to the study drug AND the cognitive data suggests a trend for possible benefit, then the results of this study will be used to plan a larger follow-up clinical trial.

Children and adults between 3 and 31 years of age with Sturge-Weber syndrome brain involvement and cognitive impairments will be eligible for this pilot study. A total of 10 patients will be enrolled at two centers including Cincinnati Children's Hospital Medical Center and the Kennedy Krieger Institute. This sample size was selected based on 1) availability of potential appropriate subjects at both centers and 2) upon the investigators experience with similar clinical trials.

Cognitive tests proposed have been previously validated in the literature and are normed to aged matched normal controls. These are published tests which are widely used. Therefore, responders in this trial will be subjects whose normed results improve on the task more than what is expected for the increase in age (6 months) +/- expected standard deviation.

Anticipated number of patients to be enrolled:

Table 4

	American Indian or Alaskan Native	Asian or Pacific Islander	Black, not of Hispanic Origin	Hispanic	White, not of Hispanic Origin	Other or Unknown	Total
Female	0	1	1	0	3		5
Male	1	0	0	1	3		5
Total	1	1	1	1	6		10

7. Data Management

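### Does ten mean ten enrolled or ten after replacement, and do replaced subjects vanish from the tolerability assessment?

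*Combined protocol and SAP*

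**What the plan says.** The Protocol Synopsis defines the target net of early losses: "Sample Size: 10 (not including subjects screened or early withdrawals within first 2 months on study drug". Section 5.7 carries this through: "Early withdrawals within the first two months on the study drug will be replaced with a new study subject".

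Three other places give ten without that exception. Section 4.3 says "The goal is to recruit up to ten participants total in this pilot study". Section 6 says "A total of 10 patients will be enrolled at two centers". Table 4, headed "Anticipated number of patients to be enrolled", adds up to ten.

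Ten also appears as an analysis count. For cognitive change the synopsis says "Mean and standard deviation of this difference for all 10 subjects will be calculated".

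On subjects who stop, section 5.7 opens with a general rule: "All data acquired prior to termination for the reasons outlined below will be included in the primary analysis unless patient withdraws consent". The list beneath it includes withdrawal of consent itself, and a later sentence of the section speaks of "withdrawal of consent for any further data submission". Safety and tolerability stand first among the primary outcome measures in the synopsis.

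**The concern.** A sample size that leaves out early withdrawals can turn into an analysis set that leaves them out. Subjects who stop in the first two months are the ones most likely to have stopped because they could not tolerate the drug. If tolerability were summarised over the ten who passed that point, early intolerance would be removed by design from a primary outcome, and the result feeds the decision on a larger trial. The completion proportion reviewed monthly under section 5.0 has the same weakness.

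Several features of the text invite this reading. Ten is used both as an accrual target and as a count of subjects analysed. No safety set is named. The replacement sentence does not say whether removals for toxicity count as withdrawals. The exception for withdrawn consent could cover someone who leaves because of side effects.

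**Working it through.** **The plan's own figure.** Table 4: female 0+1+1+0+3 = 5, male 1+0+0+1+3 = 5, total 10. The site goals give 5+5 = 10. Section 6 bases ten on availability and experience, with no effect size, SD, power or dropout rate, so no power calculation is disturbed by reading ten either way.

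**How far the two readings separate.** With *k* replacements, total enrolment is 10 + *k*. The documents give no early-withdrawal rate *d*, so 10%, 20% and 30% are assumed. The chance of at least one early withdrawal among the first ten treated is 1 − (1 − *d*)^10, and the expected number treated is 10/(1 − *d*).

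| assumed *d* | P(at least one) | expected number treated |
|---|---|---|
| 10% | 65% | 11.1 |
| 20% | 89% | 12.5 |
| 30% | 97% | 14.3 |

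The readings would probably part in practice, but by few subjects. Section 8.4 expects one subject per site every two months, that is 2 × 0.5 = 1 per month. Fourteen or fifteen subjects would then take about 15 months, longer than the 6 to 12 months stated there but inside the enrolment period of October 2016 to December 2018 (26 months).

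**What the denominator could do.** Exact (Clopper-Pearson) 95% intervals, assuming *k* early stops, all replaced, and none later:

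| *k* | stopped, over the ten | stopped, over all treated | completed, over all treated |
|---|---|---|---|
| 1 | 0/10 = 0% (0 to 31%) | 1/11 = 9% (0.2 to 41%) | 10/11 = 91% (59 to 99.8%) |
| 2 | 0/10 = 0% (0 to 31%) | 2/12 = 17% (2 to 48%) | 10/12 = 83% (52 to 98%) |
| 3 | 0/10 = 0% (0 to 31%) | 3/13 = 23% (5 to 54%) | 10/13 = 77% (46 to 95%) |

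Completion over the ten would be 10/10 (69% to 100%) in each row.

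**Which column the plan leads to.** Section 5.7 puts data acquired before termination into the primary analysis. Its list of reasons includes withdrawal by the participant and by the investigator. The replacement sentence closes a paragraph of the same section that deals with intolerable side effects, loss of seizure control and the criteria in Tables 1 and 2, so removals for toxicity fall under it on the natural reading. Sections 5.0 and 5.1 review all adverse events, section 5.5 reports all of them in aggregate, and section 8.3 has every serious event assessed continuously. None excepts replaced subjects. This leads to the all-treated columns. The completion figure in section 5.0 is paired with enrolled against projected enrolment, so its natural base is also everyone enrolled.

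**Which decisions use the proportion.** The section 6 condition asks whether any serious event possibly or probably due to the drug occurred; it is not a rate. The section 5.0 trigger is a per-participant event rate above 2 × 0.7 = 1.4 per month. The synopsis sets no numerical limit for adequate tolerability. None of these depends on whether the denominator is 10 or 12.

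**The cognitive count.** The sentence on all ten concerns only the difference in cognitive scores, and that outcome is change over six months, tested at week 26. A subject replaced within two months has at most about 2/6, or one third, of that interval, even if closing assessments are done. Adding such scores to the six-month mean would blur the outcome. In the other direction, subjects who leave after two months are not replaced, so fewer than ten may have a six-month score. The analyst reports the number actually available.

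**The case for a change.** The best counter-argument is that section 6 is the statistical section and states an enrolled total without qualification, while the only rule on keeping data speaks generally of the primary analysis and never mentions replaced subjects. A report of no discontinuations among ten reads very differently from two among twelve, and a few words would rule out the first. The consent wording is untidy as well: withdrawal of consent is both an exception to keeping data and one of the reasons for which earlier data are kept.

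Part of this stands. The section 6 sentence does omit the exception, an all-treated safety set is implied and not named, and the consent clause can be read two ways. The first is shorthand: section 4.3 calls ten a goal and ends with the same site-substitution sentence as the synopsis sample-size entry, and Table 4 is a projection. The second is filled by section 5.7 as it stands. On the third, the later and narrower phrase in section 5.7 suggests that withdrawal stops further collection. How far earlier data may be used depends on the consent form, which is not among the documents reviewed, so no rewording can be justified from here.

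**Conclusion.** The concern does not call for a change. There is a small inconsistency of wording between section 6 and the synopsis with section 5.7, and one gap that an analyst fills sensibly. Following section 5.7 and the safety sections as written, replaced subjects' adverse events stay in, and their discontinuations count against everyone treated.

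On the illustrative counts the two denominators differ by 9 to 23 percentage points, with widely overlapping intervals, and no threshold or go/no-go condition in the plan lies between them. Those sizes rest on an assumed one to three early stops, all replaced and with none later; the true number is not given. The conclusion also assumes that section 5.7 is read as a whole. A report that gave discontinuations only over the ten would depart from that section, which would be a reporting error and not a defect of the plan.
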